4.6 Prior and Concomitant Medication

The incidence of prior and concomitant medications will be presented by therapeutic area according to the Anatomical Therapeutic Chemical (ATC) level 4 classification and preferred drug name, by treatment and overall for the mITT Population.

CONFIDENTIAL

Sponsor:	Zambon S.p.A.	Protocol Number:	Z7224L01
----------	---------------	------------------	----------

Prior medications are those that started and stopped before exposure to IMP; concomitant medications are all medications taken during the study period, including those started before but on going at first IMP dose.

Where a medication start/stop date is partially or fully missing, and it is unclear as to whether the medication is prior or concomitant, it will be assumed that it is concomitant.

Notes:

- Prior and concomitant medications are all medications collected in the eCRF forms Prior and Concomitant Medications and Systemic Antibiotic Therapy.
- Medications are coded using the World Health Organisation (WHO) Drug Dictionary, WHO-DD (please refer to the final Data Management Plan for the latest coding information);
- Only the number of subjects with medications (not the number of medications) will be presented;
- If a subject has multiple occurrences of a medication, the subject will be presented only once in the respective subject count;
- Prior and concomitant medications will be summarised in separate tables;
- Medications will be displayed in descending ATC text and drug name frequency overall and then alphabetically.

4.7 Efficacy / Primary and Secondary Analysis

The analysis of the trial is on a comparative basis. For all efficacy parameters, summaries will be presented by treatment group and comparisons will be made between colistimethate sodium versus placebo. Two-sided p-values <0.05 will be considered statistically significant and 95% two-sided CIs will be presented, where appropriate.

Primary and secondary efficacy variables, where not stated differently, will be summarised for the mITT and, where relevant, PP Populations. The primary analysis will be performed on the mITT Population. Analyses conducted using the PP will be considered supportive.

The health economic variables will be analysed on the mITT Population only.

In addition, the analysis of the mean annual NCFB pulmonary exacerbation rate and the CCI will also be performed considering the subgroup of mITT subjects who were considered adherent, i.e. had an adherence of at least 80%.

4.7.1 Primary Endpoint

The primary endpoint of this trial is the mean annual NCFB pulmonary exacerbation rate. The annual NCFB pulmonary exacerbation rate will be computed for each subject as follows:

- Annual NCFB pulmonary exacerbation rate = number of NCFB pulmonary exacerbations / follow-up time (years)

CONFIDENTIAL

Sponsor:	Zambon S.p.A.	Protocol Number:	Z7224L01
----------	---------------	------------------	----------

Where NCFB pulmonary exacerbations are defined in Section 4.7.4 and follow-up time is computed as detailed in Section 4.1.7.

A pulmonary exacerbation is defined as the presence concurrently of at least 3 of the following 8 symptoms/signs for at least 24 hours:

- increased cough;
- increased sputum volume and/or consistency;
- increased sputum purulence;
- new or increased haemoptysis;
- increased wheezing;
- increased dyspnoea;
- increased fatigue/malaise;
- episodes of fever (temperature $\geq 38^{\circ}\text{C}$);

And it is clinically determined that the subject requires and is prescribed systemic antibiotic therapy.

4.7.2 Normality Assumption Checking

Not applicable.

4.7.3 Closed Testing Procedure for Primary Analysis

Not applicable.

4.7.4 Method of Analysis for Primary Endpoint

The NCFB pulmonary exacerbations collected from the Pulmonary Exacerbation eCRF form will be considered for the analysis. All cases in which the variable "Do these symptoms meet the protocol-defined criteria for NCFB pulmonary exacerbation?" is not consistent with data collected in the corresponding eCRF Pulmonary Exacerbations Symptoms form will be discussed during the blind review meeting. The decisions taken will be documented in the Blind Data Review and Analysis Sets Report.

The start of a protocol-defined NCFB pulmonary exacerbation will be taken as the first day that at least 3 of the 8 defining symptoms occurred concurrently for at least 24 hours as determined by the Investigator, as documented by the start date of the corresponding AE in the eCRF Adverse Events form and reviewed, where necessary, by the DAC (see Section 4.2.1) taking into consideration aspects such as start/stop date and associated systemic antibiotic therapy/hospitalisations.

Only NCFB pulmonary exacerbations with start date \geq date of first IMP dose and \leq date of treatment completion/discontinuation will be considered in the analysis. NCFB pulmonary exacerbations with start date = date of first IMP dose will be discussed on a case-by-case basis during the blind review of the data in order to evaluate whether they should be classified as having occurred in the screening period. The decisions taken will be documented in the Blind Data Review and Analysis Sets Report.

CONFIDENTIAL

Sponsor:	Zambon S.p.A.	Protocol Number:	Z7224L01
----------	---------------	------------------	----------

Resolution of a NCFB pulmonary exacerbation is defined as the date of completion of the required course(s) of antibiotic treatment, as collected in the eCRF Systemic Antibiotic Therapy form, and/or the Investigator's judgement that the NCFB pulmonary exacerbation has resolved, as documented by the end date provided for the corresponding AE in the eCRF Adverse Events form, whichever is the later of the two dates. If more than one systemic antibiotic therapy is administered for a NCFB pulmonary exacerbation, then the latest end date will be considered as the date of completion of the required course of antibiotic treatment.

In the case of a partial onset date of NCFB pulmonary exacerbation due to missing day, the onset of the event will be assumed to be the first day of the month. If the resultant derived date is prior to the date of first IMP dose, then it will be assumed to be equal to the first IMP dose date. Resultant derived dates will be reviewed during the blind review meeting and documented in the Blind Data Review and Analysis Sets Report.

In case of a partial resolution date of NCFB pulmonary exacerbation due to missing day, the resolution of the event will be assumed to be the last day of the month. If the resultant derived date is after the treatment completion/discontinuation date, then it will be assumed to be equal to the treatment completion/discontinuation date.

In case a NCFB pulmonary exacerbation presents a symptom with missing duration, following a conservative approach, the longest duration based on the start and stop dates of that symptom and until the resolution date of the NCFB pulmonary exacerbation will be imputed.

Two NCFB pulmonary exacerbations will be considered as a single episode in the statistical analysis if the second exacerbation started less than 14 days after the end of the systemic antibiotic therapy for the previous exacerbation (start date of the exacerbation - end date of the treatment of the previous exacerbation < 14 days). In case of more than two exacerbations for the same subject, this rule will be applied iteratively (therefore, more than two exacerbations may be considered as a single episode). Such cases will be discussed during the blind review of the data and the decisions taken will be documented in the Blind Data Review and Analysis Sets Report.

The above rule will not apply to the analysis of NCFB pulmonary exacerbations as AEs in the safety analysis.

In case of NCFB pulmonary exacerbations considered as a single episode:

- the start date of the first event will be considered as the start date;
- the stop date of the last event will be considered as the stop date;
- a worst case approach will be considered for duration of symptoms and requirement of hospitalisation. For example, if one of two exacerbations considered as a single episode has/have increased dyspnoea for ≥ 24 hours and < 48 hours and the other one has increased dyspnoea for ≥ 48 hours, the single episode will be considered in the analysis as having dyspnoea for ≥ 48 hours.

In order to investigate whether the use of inhaled colistimethate sodium reduces the frequency of pulmonary exacerbations compared to placebo in subjects with NCFB chronically infected with *P. aeruginosa*, the following hypothesis will be tested:

- Null hypothesis: there is no difference between inhaled colistimethate sodium and placebo as regards the effect on the pulmonary exacerbation rate

CONFIDENTIAL

Sponsor:	Zambon S.p.A.	Protocol Number:	Z7224L01
----------	---------------	------------------	----------

- Alternative hypothesis: inhaled colistimethate sodium reduces the pulmonary exacerbation rate in favour of inhaled colistimethate sodium compared to placebo.

The null hypothesis must be rejected for the efficacy of inhaled colistimethate sodium to be considered demonstrated.

The number and the percentage of subjects with NCFB pulmonary exacerbations, the number of NCFB pulmonary exacerbations and the total follow-up time in years, as defined in [Section 4.1.7](#), will be summarised by treatment group.

The number of NCFB pulmonary exacerbations during the treatment period will be analysed using a negative binomial model including treatment, pooled site, i.e. country, as detailed in [Section 4.9.1](#), and use of stable concomitant therapy with oral macrolides as fixed effects and log-time on treatment as an offset. If there is a significant p-value ($p < 0.05$) observed for the country covariate in this primary analysis then the number of NCFB pulmonary exacerbations during the treatment period will also be analysed using a negative binomial model for each country separately with use of stable concomitant therapy with oral macrolides as a fixed effect and log-time on treatment as an offset.

The adjusted mean annual NCFB pulmonary exacerbation rates in each treatment group and the adjusted rate ratio with their 95% CIs will be estimated by the model. OBSMARGINS option will be used for the estimates. The number of subjects considered in the model will be provided by treatment group. An adjusted rate ratio < 1 will indicate that colistimethate sodium decreases the rate of pulmonary exacerbations compared to placebo. A two-sided Wald chi-square test p-value of < 0.05 will be considered statistically significant. P-values of the effects based on Wald chi-square test will also be presented.

The log-time on treatment in years will be calculated using the following formula:

- $\text{Log-time on treatment} = \ln(\text{Follow-up time})$.

The number and the percentage of subjects with 0, 1, 2 or > 2 pulmonary exacerbations will be presented.

The number and the percentage of subjects with pulmonary exacerbations, the number of pulmonary exacerbations and the pulmonary exacerbation rate per subject per year will also be presented by treatment group for severe (defined as those requiring intravenous antibiotics and/or hospitalisation) and not severe exacerbations.

The rate of pulmonary exacerbations per subject per year will be calculated for each treatment using a weighted approach (which consists of pooling all subjects in a treatment group and dividing the total number of pulmonary exacerbations by the total follow-up time).

The total duration of systemic antibiotic therapy, overall and by route, will be summarised by treatment group using descriptive statistics for continuous variables as well as distribution frequencies for the following categorisations:

- 1-7 days;
- 8-15 days;
- 16-30 days;
- > 30 days;
- Not Evaluable.

CONFIDENTIAL

Sponsor:	Zambon S.p.A.	Protocol Number:	Z7224L01
----------	---------------	------------------	----------

Results will be reported overall and by country.

The duration of the treatment will be evaluated considering the start and end date of the therapy associated with the pulmonary exacerbation. The duration of each course of systemic antibiotic therapy will be calculated using the following formula:

- Duration (days) = stop date – start date +1

For exacerbations treated with more than one systemic treatment, the duration will be calculated by summing the duration of the associated treatments. The overlapping days will be counted only once.

It is expected that all systemic antibiotic therapy will have completed (i.e. will have a stop date) at the end of the study when data are final, as all therapy stop dates are required to be known in order to derive the resolution date of pulmonary exacerbations per the definition described earlier in this section.

In order to calculate the duration of each course of systemic antibiotic therapy, the following rules will be applied for partial dates of start and stop date of systemic antibiotic therapies:

For the start date:

- if only the day is missing, the first day of the month will be assumed. If the resulting derived date is prior to the start date of the exacerbation, then start date of therapy will be assumed to be equal to the start date of the pulmonary exacerbation.
- if the day and the month are missing, then the date will not be imputed and the duration will be classified as “Not Evaluable”.

For the stop date:

- if only the day is missing, the last day of the month will be assumed;
- if the day and the month are missing, then the date will not be imputed and the duration will be classified as “Not Evaluable”.

Resultant dates will be discussed during the blind review meeting and documented in the Blind Data Review and Analysis Sets Report.

The above summary/analysis will be performed using the mITT Population and, where appropriate, the PP Population. Results for the PP Population will be considered as supportive.

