9.1.5. EFFICACY EVALUATIONS

Pulmonary Exacerbations

The primary efficacy assessment for an individual subject is the frequency of pulmonary exacerbations.

A pulmonary exacerbation is defined as the presence concurrently of at least 3 of the following 8 symptoms/signs for at least 24 hours:

- increased cough;
- increased sputum volume and/or consistency;
- increased sputum purulence;
- new or increased haemoptysis;
- increased wheezing;
- increased dyspnoea;
- increased fatigue/malaise;
- episodes of fever (temperature $\geq 38^{\circ}\text{C}$).

And:

it is clinically determined that the subject requires and is prescribed systemic antibiotic therapy.

The start date of a protocol-defined pulmonary exacerbation will be taken as the first day that at least 3 of the pre-defined 8 symptoms/signs occurred concurrently for at least 24 hours, as determined by the Investigator.

Resolution of a pulmonary exacerbation is defined as the date of completion of the required course(s) of systemic antibiotic treatment and/or the Investigator's judgment that the NCFB pulmonary exacerbation has resolved, whichever is the later of the two dates. The exacerbation end date will be reported at the next scheduled visit or by phone.

A new pulmonary exacerbation is only considered to occur if there are at least 14 days between the end of the course of systemic antibiotics and the onset of new qualifying symptoms. If the subject is not better at the end of an initial 14-day course of systemic antibiotics, then the antibiotic should be continued for an additional standard treatment period (or escalated to intravenous therapy) in accordance with standard clinical practice.

The treatment of pulmonary exacerbations will follow current treatment regimens used at the respective participating investigational site.

Procedures to be followed in case a subject experiences symptoms suggestive of a pulmonary exacerbation are described in [Section 8.8](#) (Exacerbation Visit/Contact).

CCI

In this trial, CCI

The CCI is a validated 50-item symptom questionnaire developed to measure health status and QoL in subjects with obstructive airway diseases [19, 20].

CCI

. Scores will be collected for these 3 domains and the Total score will be produced.

The CCI is a validated self-administered, patient reported outcome measure assessing CCI for subjects with NCFB [21, 22].

CCI

and was developed for use in clinical trials and routine clinical practice.

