2.1 Primary Endpoint

The primary endpoint of this trial is the mean annual NCFB pulmonary exacerbation rate.

A pulmonary exacerbation is defined as the presence concurrently of at least 3 of the following 8 symptoms/signs for at least 24 hours:

- increased cough;
- increased sputum volume and/or consistency;
- increased sputum purulence;
- new or increased haemoptysis;
- increased wheezing;
- increased dyspnoea;
- increased fatigue/malaise;
- episodes of fever (temperature $\geq 38^{\circ}\text{C}$);

And it is clinically determined that the subject requires and is prescribed systemic antibiotic therapy.

The start date of a protocol-defined pulmonary exacerbation will be taken as the first day that at least 3 of the pre-defined 8 symptoms/signs occurred concurrently for at least 24 hours, as determined by the Investigator, as documented by the start date of the corresponding AE in the eCRF AE form.

Resolution of a pulmonary exacerbation is defined as the date of completion of the required course(s) of systemic antibiotic treatment and/or the Investigator's judgement that the NCFB pulmonary exacerbation has resolved, as documented by the end date provided for the corresponding AE in the eCRF AE form, whichever is the later of the two dates. The exacerbation end date will be reported at the next scheduled visit or by phone. A new pulmonary exacerbation is only considered to occur if there are at least 14 days between the end of the course of systemic antibiotics and the onset of new qualifying symptoms.

The treatment of pulmonary exacerbations will follow current treatment regimens used at the respective participating investigational site.

A supportive analysis will be conducted using an alternative definition of NCFB pulmonary exacerbation. The re-classification of exacerbations will be done in a blinded fashion (before

CONFIDENTIAL

Sponsor:	Zambon S.p.A.	Protocol Number:	Z7224L01
----------	---------------	------------------	----------

database lock). Alternative definition of pulmonary exacerbation: deterioration in three or more of the following key symptoms for at least 48 hours:

- Cough;
- Sputum volume and/or consistency;
- Sputum purulence;
- Breathlessness and/or exercise tolerance (dyspnoea);
- Fatigue and/or malaise;
- Haemoptysis;

And a physician determines a change in bronchiectasis treatment is required when other potential causes of clinical deterioration have been discounted.

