4.7.6.6 CCI

The CCI will be presented by treatment group.

It will be computed with the following formula:

$$\text{CCI} = \frac{(\text{follow-up time [days]} - \text{sum of durations of CCI})}{\text{follow-up time (years)}}$$

Follow-up time will be computed as detailed in Section 4.1.7.

For CCI with a resolution date after the treatment completion/discontinuation, the number of days of duration after the treatment completion/discontinuation, i.e. out of the follow-up period, will be subtracted from the sum of durations of CCI.

Non-parametric ANCOVA model with a randomisation-based methodology as proposed by Koch et al [4] will be used to analyse the ratio of the means between colistimethate sodium and placebo adjusting for any covariates effect and test the null hypothesis of the ratio of means equal to 1. Considering the sample size foreseen for this analysis, there won't be any correction for type I error. A LOGRATIO conversion will be applied.

The model will include treatment group, pooled site, i.e. country, as detailed in Section 4.9.1, and use of stable concomitant therapy with oral macrolides as covariates. No stratification variable will be included.

Treatment effect coefficient will be presented along with standard error, associated test statistic and two-sided p-value. A two-sided p-value of <0.05 will be considered statistically significant.

Treatment effect coefficient and associated 95% CI will be exponentiated to obtain estimates and 95% CI for the ratio of the means.

Due to the fact that the p-value computation is based on the re-randomisation of the population, while the CI is based on repeated random sampling theory, there might be disagreement regarding the treatment effect using these two different approaches. Even if these occurrences are quite infrequent, it's worth stating that the p-value from the randomisation test is based on a more realistic and minimal assumptions and should take precedence [5].

CONFIDENTIAL

Sponsor:	Zambon S.p.A.	Protocol Number:	Z7224L01
----------	---------------	------------------	----------

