  'Col. Sodium / Placebo: Visit 6' 0 0 1 0 0 0 -1 0,
  'Col. Sodium / Placebo: Visit 7' 0 0 0 1 0 0 0 -1 / cl;
  BY byvar; (optional)
  WHERE wherever; (optional)
RUN;
```

Notes:

- Visit represents the clinic visit;
- Psite represents the pooled site, i.e. country, as detailed in [Section 4.9.1](#);
- Med represents use of stable concomitant therapy with oral macrolides (e.g. azithromycin or erythromycin or clarithromycin) (Yes/No);
- Sub represents the Subject Number;
- Change represents the change from baseline to each visit of the variable;
- Baseline represents the baseline value of the variable;
- Treatment order: 1= Colistimethate Sodium, 2= Placebo.

CONFIDENTIAL

Sponsor:	Zambon S.p.A.	Protocol Number:	Z7224L01
----------	---------------	------------------	----------

- **Tables that require Prentice, Williams and Peterson Total Time model and 95% CIs of hazard ratios between treatments:**

```
PROC PHREG data=dset;
  CLASS treatment psite med;
  MODEL (tstart , tstop)*status(1) = treatment psite med / ties=Breslow;
  STRATA episode;
  HAZARDRATIO 'Col. Sodium vs Placebo' treatment / cl=both;
  BY byvar; (optional)
  WHERE wherever; (optional)
RUN;
```

Notes:

- Psite represents the pooled site, i.e. country, as detailed in [Section 4.9.1](#);
- Med represents use of stable concomitant therapy with oral macrolides (e.g. azithromycin or erythromycin or clarithromycin) (Yes/No);
- Status represents the censoring indicator (1 = censored);
- Treatment order: 1= Colistimethate Sodium, 2= Placebo;
- Dataset for the analysis should be adequately created: Subjects with no events have a single observation, while subjects with one event have two rows etc... A pair of variables (tstart, tstop) is used to define the time interval of risk. The start time (tstart) is generally equal to 0 for the first event and equals to the last recurrence stop time for further events. During an episode of pulmonary exacerbation, the subjects can't have another episode. Therefore, they are by definition not at risk for a next event during a previous episode. The stop time (tstop) is a recurrent event time (status = 1) or a censored time (status = 0). The event order should be denoted by variable episode.

- **Multiple Imputation for pulmonary exacerbation rate**

An example of SAS code is provided below for the **CCI** analyses pulmonary exacerbation rate.

Missing at random and copy reference imputation

```
PROC GENMOD DATA=dataset1;

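### Two exacerbations that the plan keeps separate can overlap in time, and SAP 4.7.6.6 then subtracts the shared days twice while the PWP data set in SAP 4.14 receives an impossible interval

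*SAP*

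**What the plan says.** **When an episode ends.** SAP 4.7.4 begins: "Resolution of a NCFB pulmonary exacerbation is defined as the date of completion of the required course(s) of antibiotic treatment". It adds the investigator's judgement of resolution, taken from the adverse event end date, and uses "whichever is the later of the two dates". If the day of the resolution date is missing, the date is set to the end of that month, capped at the end of treatment.

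**When a second event is separate.** The test in SAP 4.7.4 uses another date. Two events are joined only if "start date of the exacerbation - end date of the treatment of the previous exacerbation < 14 days". SAP 2.1 has the same anchor ("A new pulmonary exacerbation is only considered to occur if there are at least 14 days between the end of the course of systemic antibiotics"). Protocol 9.1.5 has it too, requiring "at least 14 days between the end of the course of systemic antibiotics and the onset of new qualifying symptoms". Protocol 8.7 and 18.4.2 agree. None of these places mentions resolution of the first event.

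**What is done with durations.** SAP 4.7.6.6 takes follow-up days minus the sum of event durations and divides by follow-up years. The endpoint's name is redacted but the formula is legible. Its only visible correction concerns days after treatment ends, which, being "out of the follow-up period, will be subtracted from the sum of durations of" the events, do not count. Nothing is said about days shared by two events. For antibiotic courses within one exacerbation, SAP 4.7.4 does have such a rule: "The overlapping days will be counted only once".

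**What the PWP data set assumes.** The notes in SAP 4.14 say: "During an episode of pulmonary exacerbation, the subjects can't have another episode". Each later risk interval starts at the stop time of the previous recurrence.

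**The concern.** The end of an episode and the test for a new one run on different clocks. Between the 14th day after antibiotics and the resolution date there is a window in which a new onset counts as a second event although the first is still open by the SAP's own definition. The two intervals then overlap.

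Two derivations rely on this not happening. The formula in 4.7.6.6 is correct only if durations are disjoint; otherwise it gives too few event-free days. The PWP intervals are valid only if each onset comes after the previous resolution; otherwise the interval has zero or negative length. At stake are the value of a secondary endpoint for the subjects concerned, and whether the PWP model can use every event that the primary model counts.

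**Working it through.** The plan gives no figure for overlap, so there is none to reproduce. The check applies the written rules to assumed timelines, counting days inclusively.

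**Example.** Day 1 is the onset of the first event; shifting all days by a constant changes nothing below.
- Event 1: onset day 1, antibiotics end day 14, judged resolved day 40.
- Event 2: onset day 30 with its own systemic antibiotic, resolved day 50.

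1. Merge test (SAP 4.7.4): 30 − 14 = 16, which is not below 14, so two events are kept.
2. Durations: 40 − 1 + 1 = 40 and 50 − 30 + 1 = 21; sum 61.
3. Distinct days affected: 1 to 50, that is 50.
4. Subtracted twice: 61 − 50 = 11 (days 30 to 40).
5. With 365 days of follow-up, the SAP formula gives (365 − 61) / (365 / 365.25) = 304.2 days a year. Distinct days give (365 − 50) / (365 / 365.25) = 315.2.
6. PWP interval for event 2: start = stop of event 1 = 40, stop = onset of event 2 = 30. The start is after the stop.

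**Boundaries.** In a second assumed timeline, event 1 starts on day 100 with antibiotics to day 113, and event 2 resolves on day 145.

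| Event 1 resolves | Event 2 onset | Days after antibiotics | Events | Sum of durations | Distinct days | Counted twice |
|---|---|---|---|---|---|---|
| 141 | 126 | 13 | 1 | 46 | 46 | 0 |
| 141 | 127 | 14 | 2 | 35 − 35 + 42 + 19 = 61 | 46 | 15 |
| 141 | 129 | 16 | 2 | 42 + 17 = 59 | 46 | 13 |
| 120 | 129 | 16 | 2 | 21 + 17 = 38 | 38 | 0 |

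The problem therefore needs both an onset at least 14 days after antibiotics and a resolution date on or after that onset.

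**Overlap created by imputation.** Assume antibiotics end on 5 May, the resolution date is recorded only as May and so becomes 31 May, and a second event starts on 20 May and lasts at least to 31 May. The gap is 20 − 5 = 15 days, so two events are kept, and 20 to 31 May (12 days) is subtracted twice. A missing day is enough; no unusual clinical course is needed.

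**Scale in an arm.** If a share p of subjects has one 11-day overlap in a full year, the arm mean is too low by about 11p days: 0.22, 0.55 or 1.1 days for p = 2%, 5% or 10%. These shares are assumptions. The error in the comparison depends on how far the arms differ.

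**The case against.** The strongest objection is that such pairs should be rare. Protocol 9.1.5 has antibiotics continued or escalated if the subject is not better, which moves the anchor later. Protocol 8.7 has weekly calls until resolution. If a further course is recorded under the open exacerbation, SAP 4.7.4 uses the latest antibiotic end date and there is one event. The blinded committee in SAP 4.2.1 may ask sites to look again at classification and duration. All of this stands as a reason to expect few cases. None of it is a rule for the cases that remain: the committee only recommends, the site's investigator decides, and the blind-review sentence after the merge rule concerns events that have been merged.

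It is also fair that the antibiotic overlap rule covers courses within one exacerbation, so it is not a direct precedent, and that the PWP model is a further investigation which already caps the number of events. A cap is a stated choice, however; an interval that ends before it starts is not.

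A reader might go further and infer that the primary count depends on how late a site closes the adverse event. It does not: the merge test uses only the second onset and the first antibiotic end. In the example the count is 2 whether event 1 resolves on day 14 or day 40. Adding a merge on resolution date would itself introduce that dependence, including on imputed dates, and would depart from the protocol's event definition.

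A reader might also infer a biased treatment effect. The documents show none. With the rates in SAP 3.9, 0.8256 / 1.2701 = 0.65, and any proportional increase in counts common to both arms cancels from that ratio. No reason for a difference between arms is given.

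**Conclusion.** The point holds for two derivations. As written, 4.7.6.6 gives a wrong value whenever two kept exacerbations overlap, and 4.14 assumes away a case that 4.7.4 permits. In the example, 11 days too many are subtracted and the PWP interval runs from day 40 to day 30.

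This rests on the site recording the second episode as its own protocol-defined event with its own systemic antibiotic, on the legible formula in 4.7.6.6 (the endpoint name is redacted), and on reading the stop time of a recurrence in 4.14 as its resolution date. The frequency is unknown, so the effect on the trial's results cannot be computed. It is limited to one secondary endpoint and one exploratory model. The documents do not support a claim that the primary count or the primary rate ratio is wrong.

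**What to change.** 1. **SAP 4.7.6.6:** replace the sum of durations with the number of distinct calendar days within follow-up that fall in any exacerbation. This also covers the trimming at end of treatment.
2. **SAP 4.14:** state how an onset on or before the previous resolution date enters the PWP data set, so that no interval has a start equal to or after its stop.
3. **Reporting:** give the number of overlapping pairs by arm, and how many involve an imputed resolution date.
4. **Leave unchanged** the protocol's 14-day antibiotic anchor for the primary count.

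The cost is a few sentences, one changed derivation and one short table. Neither the event count nor the protocol definition changes. Section 2.2 of the SAP addendum says that the database is locked and the study unblinded, so any re-run must be marked post hoc, as SAP section 1 requires. If the table shows no overlapping pairs, no re-run is needed.
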